9.3 RESPONSE DEFINITIONS

9.3.1 OVERALL SURVIVAL

Overall survival (OS) is defined as the time from treatment start date to death. Patients who are still alive at the end of the study will be censored. PFS and OS will be assessed using the Kaplan-Meier method overall and by cohort.

9.3.2 INTRACRANIAL PROGRESSION FREE SURVIVAL

The time to intracranial progression, determined by modified RECIST 1.1, will be calculated from the time of study enrollment to intracranial progression (event) or the last follow-up date if the patient has not developed the intracranial progression yet (censored). The median time to intracranial progression and intracranial progression free survival rates at specific times will be estimated and reported with 95% confidence interval utilizing the method of Kaplan and Meier. This will serve as the primary analysis and will be performed overall and within each treatment group. Completing risk analysis may be considered by treating events outside of intracranial disease progression (e.g. events such as extracranial disease progression, early dropout due to toxicity, or death) as competing risks.

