The purpose of phase II part is to estimate the time to intra-cranial progression and overall survival time. In this part, we will enroll up to 24 patients into RP2D. The 6 patients treated at RP2D from phase I part of the study will be included in the Phase II part, thus resulting in a total of 30 patients at RP2D by the end of the study, with the goal of having 10 patients each of melanoma, NSCLC, and breast cancer. This phase II part is designed to collect data for future larger studies. Specifically, we would like to estimate time to intracranial progression considering death as a competing risk and overall survival time using Kaplan-Meier method, both with 95% confidence interval.

Figure 1: Study Schema

[Study Schema] – See Schedule of Assessments

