4.1.2 PHASE II PRIMARY OBJECTIVE

- Time to intracranial progression (defined as progression of existing lesions by modified RECIST 1.1) lesions and development of new
- Overall survival.

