9.2 PHASE II

The purpose of phase II part is to estimate the time to intra-cranial progression and overall survival time. In this part, we will enroll up to additional 24 patients into RP2D over the course of 12-18 months. The 6 patients treated at RP2D from phase I part of the study will be included in the Phase II part, thus resulting in a total of 30 patients at RP2D by the end of the study, with the goal of having 10 patients with each of melanoma, NSCLC, and breast cancer. This phase II part is designed to collect data for future larger studies. Specifically, we would like to estimate time to intracranial progression considering death as a competing risk and overall survival time using Kaplan-Meier method, both with 95% confidence interval.

Two dose limiting toxicities (DLT) will be monitored separately: intracranial and extracranial DLTs. If there is a high chance that probability of intracranial DLT is found to be $> 15\%$, i.e., $\text{Pr}(\text{intra-cranial DLT Rate} > 15\% | \text{Data}) > 70\%$, or the extra-cranial DLT rate of higher than 30% , i.e., $\text{Pr}(\text{extra-cranial DLT Rate} > 30\% | \text{Data}) > 70\%$, then the regimen will be considered too toxic at current dose. Results should be discussed with EMD Serono to decide if further enrollment should be started at a lower dose level. Protocol will be amended if necessary. The window for DLT evaluation will be at 4 weeks after the start of the treatment.

Given these rules and the prior for intra-cranial DLT toxicity rate as $\text{beta}(0.15, 0.85)$ and extra-cranial DLT toxicity rate as $\text{beta}(0.3, 0.7)$, we claim a dose level too toxic if any of the following happens.

Number of patients with intra-cranial DLTs/total of number of patients treated $\geq 3/10, 4/15, 5/20, 5/25, 6/30$; or

Number of patients with extra-cranial DLTs/total of number of patients treated $\geq 4/10, 6/15, 8/20, 9/25, 11/30$.

The operating characteristics based on the toxicity stopping rules for 30 patients are in Table 4. The Bayesian toxicity monitoring rule are calculated by the online Shiny application Bayesian Toxicity Monitoring using posterior probability developed by Department of Biostatistics. The operating characteristics were evaluated using codes written by statistical collaborator [name].

Table 4: Operating Characteristics (5,000 simulations)

True Intracranial DLT Rate	True Extracranial DLT Rate	P (Stop Early)	Average of Expected Sample Size
0.05	0.1	0.03	29

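### Section 9.3.2 makes Kaplan-Meier with intracranial progression as the only event the primary analysis, against the competing-risk approach of 3.0 and 9.2, mislabels the curve as intracranial PFS, and does not tie censoring to a brain MRI

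*Combined protocol and SAP*

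**What the plan says.** Section 4.1.2 names the first phase II primary endpoint: "Time to intracranial progression (defined as progression of existing lesions by modified RECIST 1.1", together with the development of new lesions. Overall survival is the other.

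On the method, section 3.0 says "we would like to estimate time to intracranial progression considering death as a competing risk", and section 9.2 repeats it: "estimate time to intracranial progression considering death as a competing risk and overall survival time using Kaplan-Meier method", each with a 95% confidence interval.

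Section 9.3.2 is headed as intracranial progression free survival. Its time variable is "calculated from the time of study enrollment to intracranial progression (event) or the last follow-up date" for patients who have not progressed in the brain, and these patients are censored. It then says "intracranial progression free survival rates at specific times will be estimated", along with the median time to intracranial progression, "utilizing the method of Kaplan and Meier. This will serve as the primary analysis". Competing risks come last and are optional: "Completing risk analysis may be considered by treating events outside of intracranial disease progression". The examples given there are extracranial progression, dropout for toxicity and death.

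Section 9.3.1 adds "PFS and OS will be assessed using the Kaplan-Meier method overall and by cohort" without defining a PFS event. Section 6.2.8 says intracranial PFS goes on being monitored after salvage radiosurgery, also without a definition.

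On follow-up, Table 3 marks no brain MRI after the discontinuation visit. Its footnote f runs MRI to the later of progression and discontinuation, without saying progression at which site. Section 8.15 has telephone follow-up every 12 weeks until death or the end of the study.

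**The concern.** An analyst cannot follow both 9.2 and 9.3.2. The only analysis that the plan calls primary is the one that leaves death out.

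Three things follow. First, if patients who die without intracranial progression are censored, one minus Kaplan-Meier estimates progression as if death could be removed. It then overstates the proportion who actually progress in the brain. Second, a curve in which death is not an event is not a progression free survival curve, and it reads too high under that name. Third, a last follow-up date that can be a telephone contact may leave patients in the risk set after anyone last looked at the brain.

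What is at stake is a reported co-primary estimate. Phase II exists to supply data for later, larger studies (9.2), and this figure would depend on which section the analyst chose to follow.

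**Working it through.** **Plan's own figure.** The phase II total at the recommended dose is 24 + 6 = 30 patients (9.2), which reproduces. The plan states no event count, power or precision for this endpoint.

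**Treatment of death, section by section.**

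| Section | Role of death without intracranial progression |
|---|---|
| 3.0 and 9.2 | competing event |
| 9.3.2, event and censoring rule (primary) | not an event; censored by implication, not stated outright |
| 9.3.2, optional analysis | one of several competing events |
| 9.3.2, heading and rate label | the name implies an event, but the definition does not |

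**Size: inputs.** The documents give no rate of death without intracranial progression and no median time to progression, so both are assumed. Hazards are constant: λp = ln2/mp for progression, with mp = 3, 4 or 6 months, and λd for death without progression. The share of first events that are deaths is s = λd/(λp+λd), set at 5%, 10% or 25%. The times are weeks 24 and 52, landmarks the plan uses for survival: t = 5.52 and 11.96 months.

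**Formulas** (censoring at the last MRI, treated as non-informative):
- One minus Kaplan-Meier, deaths censored: 1 − exp(−λp t)
- Cumulative incidence, death competing: (1 − s)(1 − exp(−(λp+λd)t))
- Intracranial PFS, death as an event: exp(−(λp+λd)t)

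**Worked case:** progression median 4 months, death median 12 months. λp = 0.1733, λd = 0.0578, s = 25%. At week 24:
- 1 − exp(−0.1733 × 5.52) = 61.6%
- 0.75 × (1 − exp(−0.2310 × 5.52)) = 54.0%
- Progression or death: 1 − exp(−0.2310 × 5.52) = 72.1%

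The first exceeds the second by 7.5 points before rounding. The curve labelled PFS reads 38.4% (100 − 61.6) where PFS is 27.9% (100 − 72.1), which is 10.5 points too high.

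**One minus Kaplan-Meier less cumulative incidence, in points, for mp = 3 / 4 / 6 months:**

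| Deaths among first events | Week 24 | Week 52 |
|---|---|---|
| 5% | 1.9 / 1.3 / 0.7 | 3.9 / 3.1 / 2.1 |
| 10% | 3.9 / 2.7 / 1.5 | 7.9 / 6.4 / 4.3 |
| 25% | 10.8 / 7.5 / 4.2 | 20.6 / 17.1 / 11.8 |

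At week 24 the curve labelled PFS exceeds PFS with death as an event by 1.7-1.9, 3.6-3.9 and 9.7-10.5 points for the same three shares.

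**Sampling error.** With 30 patients and a proportion near 50%, the half-width is 1.96 × √(0.25/30) = 0.179, about 18 points.

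**Censoring date.** Keep medians 4 and 12. Suppose that MRI stops at a constant hazard λc, with median 6, 12 or 24 months, that progression is unseen afterwards, and that telephone contact keeps patients at risk. With deaths censored, one minus Kaplan-Meier becomes λp/(λp+λc) × (1 − exp(−(λp+λc)t)). At week 24 this is 47.8%, 54.0% or 57.6%, against a cumulative incidence of 54.0%: from 6.2 points too low to 3.6 too high. The direction is therefore not fixed once telephone contacts count. A competing-risk estimate that counts all deaths and keeps stopped patients at risk gives λp/(λp+λd+λc) × (1 − exp(−(λp+λd+λc)t)), which is 42.6%, 47.8% or 50.8%.

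**The case against.** **The sections can be harmonised.** The 9.2 sentence could be parsed as Kaplan-Meier for both endpoints, and 9.3.2 does mention competing risks. But that parsing conflicts with death as a competing risk in the same sentence. The mention in 9.3.2 is optional and lists more competing events. The contradiction stands.

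**Intracranial status need not be lost.** A reader might infer that patients who stop treatment go unscanned and have unknown intracranial status. The documents do not establish this. Footnote f and 8.1.4 continue MRI to the later of progression and discontinuation, so a patient who stops without progression is still scanned. If progression there means intracranial progression, most of the gap closes; if it means any site, a patient stopping at extracranial progression may have no further scheduled MRI. Section 8.13 also encourages patients who stop to attend remaining visits, the investigator may add scans, and the intracranial part of Appendix 2 allows progression to be called on clinical grounds. What remains is an unstated censoring date, with a gap of at least the interval since the last scan. The MRI-stop model above is therefore an adverse case.

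**The competing-risk analysis is not automatically closer to the truth.** In that adverse case, counting every death while MRI has ended is further from 54.0% at MRI-stop medians of 6 and 12 months, and similar at 24. This is fair, and it is why the fix includes the censoring date and a sensitivity analysis.

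**Three operative definitions.** A reader might infer these from 9.3.2. The death-as-event reading rests only on a heading and a rate label, while the paragraph's own event rule contradicts it. It is a labelling error.

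**Few deaths may come first.** Section 1.2 attributes nearly 95% of deaths to brain metastasis in melanoma patients with such disease. That points to the low end of the table for melanoma, the target for 10 of the 30 patients.

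**Conclusion.** The point holds. The primary analysis in 9.3.2 contradicts 3.0 and 9.2, the intracranial PFS label is wrong for the curve described, and the censoring date is not tied to a scan. Confidence is high for the first two. How much the third matters depends on how footnote f is read.

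The size is illustrative only. It rests on constant hazards, progression medians of 3 to 6 months, assumed death shares and non-informative censoring at the last MRI. A reader might take the largest figure in the table, 20.6 points at week 52, as a ceiling for a 25% share. It is not: a 2-month progression median at the same share gives 23.7. Nor do the documents support treating a large gap as expected, since they give no death share at all.

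A reader might also infer that a trial decision is at risk. Phase II has no efficacy decision rule, and no dose, enrolment or stopping decision uses this estimate. Most of the gaps are smaller than the 18-point half-width. They are nevertheless systematic differences in what is being estimated, in a phase whose purpose is estimation. This should be corrected before analysis, so that the choice cannot follow the data.

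**What to change.** In 9.3.2:
- Make the primary analysis the cumulative incidence of intracranial progression, with death as the competing event and a 95% confidence interval, as 3.0 and 9.2 already state.
- Censor patients with neither intracranial progression nor death at the last evaluable brain MRI.
- Wherever intracranial PFS is reported (6.2.8, 9.3.1, 9.3.2), define it separately with death as an event and estimate it by Kaplan-Meier.
- Keep any analysis that adds extracranial progression or toxicity dropout as competing events as a labelled secondary analysis.
- Add a sensitivity analysis for deaths long after the last MRI: counted as competing events, or censored at that MRI. The window is for the sponsor's statistician to fix before analysis; 3.0 and 9.2 do not prescribe one.

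The cost is wording in 9.3.1 and 9.3.2. The dates of the last evaluable brain MRI and of death come from scans and follow-up already planned. No new visits or patients are needed.

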9.3.3 TOXICITY

The intracranial and extracranial toxicities and DLTs will be summarized by grade, relationship, time during the treatment, etc., for each dose in each group.

9.3.4 EXTRACRANIAL PROGRESSION

The time to extracranial progression, determined by RECIST 1.1 criteria, will be calculated from the time of study enrollment to extracranial progression (event) or the last follow-up date if the patient has not developed the extracranial progression yet (censored). The cumulative incidence rate may be estimated by competing risk analysis treating events outside of extracranial disease progression (e.g. events such as intracranial disease progression, early dropout due to toxicity, or death) as competing risks.

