4.2 SECONDARY OBJECTIVES

- Intracranial progression 4, 8, 12, 16 weeks and every 8 weeks thereafter.
- Intracranial objective response rate as measured by RANO-BM, iRANO, and RECIST 1.1.
- Time to second intracranial progression after Salvage SRS
- Overall survival rate at 24, 52 and 68 weeks.
- Frequency of grade 3+ intracranial toxicities at 4, 12, 24, 36, 52, and 68 weeks. Frequency of extracranial progression and response rate at 8, 16, 24, every 8 weeks.
- Frequency of neurocognitive decline 12, 24, 36 weeks (optional). Changes in neurocognitive function and health-related quality of life.
- Dose, duration and frequency of steroid use for symptomatic management.
- Evaluation of safety and tolerability of pimasertib/bintrafusp alfa combination

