6.2.8 PERMITTED THERAPIES: SRT

For patients that are deriving clinical benefit from protocol treatment, but having evidence of progression in brain lesions that are amenable to SRS, treatment with SRS is allowed and patients can remain on systemic therapy. Patients will be censored for brain metastasis response unless one measurable lesion remains unirradiated. Patients will continue to be monitored for intracranial PFS.

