- e Prothrombin time/International Normalized Ratio, Activated Partial thromboplastin time.
- f MRI Scan will be performed every 4 weeks for the first 16 weeks, then every 8 weeks until progression or discontinuation of study treatment, whichever comes later. Imaging window is \pm 7 days. If scans performed within 4 weeks of discontinuation, repeat scans are not required.
CT-CAP or PET-CT will be performed every 8 weeks until progression or discontinuation of study treatment, whichever comes later. Imaging window is \pm 7 days. If scans performed within 4 weeks of discontinuation, repeat scans are not required.
Please note that if an MRI, CT chest/abdomen/pelvis or PET-CT is not already performed as standard of care per Schedule of Assessments in Section 8.1.4, the investigator may choose to perform either or both procedures for assessing progress of the patient.
- g Obtain archival only if tissue is post PD-1 exposure for melanoma and lung cancer patients. See Section 8.7.1 for additional details.
- h Patients with biopsiable extracranial disease may have tissue collected. See Section 8.8.
- i Cerebrospinal Fluid may be obtained if testing for LMD. See section 8.7.3 for additional details.
- j See Section 8.7.
- k CBC & CMP is done every 2 weeks (+/- 7 days) prior to infusion.
- l Patients will have ophthalmological evaluation at baseline and every 12 weeks. See section 8.3.
while receiving protocol therapy
- m Serum chemistry includes the tests listed (glucose, BUN, creatinine, sodium, potassium, magnesium, chloride, bicarbconate, calcium, phosphorus, total and direct bilirubin, ALT, AST, ALP, LDH, total protein, albumin, CPK, and uric acid). CMP is done every 2 weeks prior to infusion.
- n Height only taken at Screening
- o There will also be a Neurocognitive exam at the 3-month mark
- p A follow up call will be done at 90 days to assess patient safety.

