8.10 MANAGEMENT OF PATIENTS WITH DISEASE PROGRESSION

In the absence of unacceptable toxicity, patients who meet criteria for disease progression will be permitted to continue study treatment if they meet all of the following criteria:

- Evidence of clinical benefit, as determined by the principal investigator following a review of all available data
- Absence of symptoms and signs (including laboratory values) indicating unequivocal progression of disease
- Absence of decline in ECOG Performance Status that can be attributed to disease progression
- Absence of tumor progression at critical anatomical sites (e.g., leptomeningeal disease) that cannot be managed by protocol-allowed medical interventions

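### Section 9.3.4 allows intracranial progression and toxicity dropout to count as competing risks for extracranial progression; the result is a first-event incidence that cannot exceed, and will usually understate, the frequency the secondary objective asks for

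*Combined protocol and SAP*

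**What the plan says.** Section 9.3.4 defines time to extracranial progression from enrollment to the event, or to "the last follow-up date if the patient has not developed the extracranial progression yet (censored"). It then turns to estimation: "The cumulative incidence rate may be estimated by competing risk analysis treating events outside of extracranial disease progression", with the illustration "e.g. events such as intracranial disease progression, early dropout due to toxicity, or death) as competing risks". No other estimator is named for this endpoint.

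The objective served is in section 4.2: "Frequency of extracranial progression and response rate at 8, 16, 24, every 8 weeks". It asks how often extracranial progression occurs by fixed weeks and does not restrict this to first events.

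Other sections describe what happens after the two non-fatal events:
- Section 6.2.8, for patients who are benefiting and whose progressing brain lesions suit radiosurgery: "treatment with SRS is allowed and patients can remain on systemic therapy".
- Section 8.10: "patients who meet criteria for disease progression will be permitted to continue study treatment if they meet all of the following criteria".
- Table 3, footnote f: "CT-CAP or PET-CT will be performed every 8 weeks until progression or discontinuation of study treatment, whichever comes later".
- Table 3, footnote b, moves patients who stop for reasons other than progression into scheduled follow-up visits. Section 8.13 encourages those who withdraw from treatment to attend the remaining visits.

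For the primary time-to-intracranial-progression endpoint, sections 3.0 and 9.2 name death alone as the competing risk.

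**The concern.** A competing event is one after which the event of interest can no longer happen. Death qualifies. Brain progression and stopping drug for toxicity do not, because the patient can still progress outside the brain and, for at least part of the time, is still being scanned. If these are coded as competing events, such a patient leaves the risk set and any later extracranial progression goes uncounted.

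What is at stake is interpretation. Reported as the frequency of extracranial progression, a first-event incidence makes extracranial control look better than it is, most of all where brain progression is common. Tumor-type cohorts with different rates of brain progression could then appear to differ in extracranial control for that reason alone. Section 9.2 says that phase II is meant to inform larger studies, so the figure may well be carried forward.

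**Working it through.** **Is there a figure to reproduce?** No. The documents give no rate or hazard for extracranial progression, so every rate below is an assumption.

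**Direction, which needs no rates.** Patients whose extracranial progression comes before brain progression, toxicity dropout and death are a subset of those whose extracranial progression comes before death. So the first-event incidence cannot exceed the death-only incidence at any time. The two are equal only if no patient has extracranial progression after one of the other two events.

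**Size, by illustration.** Assume constant, independent cause-specific hazards and complete ascertainment. Assumed medians are 6 months for extracranial progression (E), 4 for intracranial progression (I), 12 for death (D) and 24 for toxicity dropout (T). Each hazard is ln 2 / median:
- h_E = 0.1155, h_I = 0.1733, h_D = 0.0578, h_T = 0.0289 per month.

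Cumulative incidence at t months is CIF(t) = (h_E / H) × (1 − exp(−H t)), where
- as listed in 9.3.4: H = h_E + h_I + h_D + h_T = 0.3755, h_E / H = 0.3077;
- death only: H = h_E + h_D = 0.1733, h_E / H = 0.6667.

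Week 24 is 24 × 12/52 = 5.54 months:
- as listed: 0.3077 × (1 − 0.1250) = 0.27
- death only: 0.6667 × (1 − 0.3830) = 0.41

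Week 52 is 12 months:
- as listed: 0.3077 × (1 − 0.0110) = 0.30
- death only: 0.6667 × (1 − 0.1250) = 0.58

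The same formula at other weeks on the objective's 8-weekly grid, as listed against death only:
- week 8: 0.15 and 0.18
- week 16: 0.23 and 0.32
- week 48: 0.30 and 0.57

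**Which event drives the gap?** With toxicity dropout and death competing but not intracranial progression, H = 0.2022 and h_E / H = 0.5714. This gives 0.38 at week 24 and 0.52 at week 52, much nearer the death-only values. Intracranial progression accounts for most of the difference.

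**Other assumptions.**
- Medians of 8/5/12/24 months (E/I/D/T): 0.27 and 0.49 at week 52. Medians of 6/6/18/24: 0.38 and 0.63.
- Extracranial median 6 and death median 12 months, intracranial median varied from 3 to 10 months and toxicity dropout from 20% to 5% by 6 months: 23.9% to 34.6% as listed against 41.1% at week 24, and 26.0% to 43.7% against 58.3% at week 52.

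**Visit schedule.** Brain imaging is the more frequent early on: "MRI Scan will be performed every 4 weeks for the first 16 weeks, then every 8 weeks", against body imaging every 8 weeks in the same footnote. Section 9.3.4 has no rule for progression in both compartments at the same visit. A simulation of 200,000 patients on this schedule used medians of 6 (E), 5 (I) and 12 (D) months and 10% dropout by 6 months. At week 24 it gave 39.0% for death only. The listed analysis gave 27.7% if ties count as extracranial and 23.8% if they count as intracranial. With a shared gamma frailty of variance 1 replacing independence, the figures were 30.1%, 20.5% and 17.3%. The gap therefore does not depend on assuming independence.

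**The case against.** **The analysis is optional.** A reader might infer that the plan requires this estimator and ends extracranial follow-up at brain progression. The text does not support that. Estimation is worded as something that may be done, the competing events are examples, and the definite sentence in 9.3.4 follows patients to extracranial progression or last follow-up. This stands. But no other estimator is named, and an open list leaves the target quantity to be settled after the data are seen.

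**A first-event incidence is a legitimate quantity.** It is, and correctly labelled it would not be biased. The fault is the mismatch with section 4.2, which does not ask for it.

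**Not every patient stays observable.** A reader might also infer that all patients with brain progression have radiosurgery, remain on drug and keep being scanned, so that the correction is wording alone. Sections 6.2.8 and 8.10 make continuation conditional. Footnote f does not say which compartment's progression it means, the CT row of Table 3 has no mark in the post-treatment columns, and section 8.1.4 describes body imaging as clinically indicated and on a different timetable. Extracranial scans after discontinuation are therefore not secured. This stands. It limits how fully the death-only quantity can be observed, but does not make brain progression a competing event.

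**Toxicity dropout matters little and is ambiguous.** It could mean stopping drug or leaving the study. Stopping drug leaves the patient at risk; leaving the study is a censoring question. The text should separate the two.

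**It is a secondary, descriptive endpoint** in about 30 patients, and no decision rule uses it. True, and this bounds the importance of the point.

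**Conclusion.** The point holds as a mismatch between the estimator that 9.3.4 offers and the objective in 4.2. Of the listed competing risks, only death precludes extracranial progression, and the protocol itself uses death alone for its primary progression endpoint. The direction follows from the definitions and is certain where follow-up continues. The size is illustrative: about 0.27 against 0.41 at week 24 and 0.30 against 0.58 at week 52. These figures rest on assumed medians, constant independent hazards and complete ascertainment after brain progression, and the gap is smaller at early visits. Week 52 is also not on the objective's 8-weekly grid, so weeks 24 and 48 are the more relevant comparisons. The documents do not support reading these numbers as the bias this trial will show. The change is worth making before analysis, as an improvement to a secondary endpoint.

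**What to change.** In section 9.3.4:
- Count the first extracranial progression whether or not intracranial progression, radiosurgery or stopping treatment for toxicity came earlier.
- Make death without extracranial progression the only competing event, and report the Aalen-Johansen cumulative incidence with a 95% CI at the weeks in section 4.2.
- Censor at the last body scan if imaging stops or the patient leaves the study. Add a sensitivity analysis, because imaging may stop as a consequence of brain progression and that censoring may be informative.
- Label any first-event analysis as such, with a rule for progression in both compartments at the same visit.

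Reconcile Table 3 footnote f, the post-treatment columns of Table 3 and section 8.1.4 on how long body imaging continues and which progression ends it. The competing-risk sentence in section 9.3.2 mirrors this one and should be checked in the same way.

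The cost is some analysis work and a clarification of the imaging text. Ascertainment will remain incomplete in patients whose body imaging stops after brain progression, and the report should say how many there were.
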